9.2 SAMPLE SIZE

Upon conclusion of the pilot, further recruitment to the study will occur with a planned interim analysis for futility and efficacy. Participants in the pilot study will continue to have their data analysed. The planned interim analysis is referred to as ‘stage 1’ analysis for convenience. The final analysis is referred to as ‘stage 2’ analysis. In each stage, there are three co-primary endpoints:

1. sensitivity (of the Avantect test),
2. specificity (of the Avantect test) and

3. resectability of diagnosed PCs

In the stage 1 interim analysis, these endpoints will be assessed within the intervention arm, as more information will be available on the diagnostic status of this group. In the stage 2 final analysis, the sensitivity and specificity of the test will be estimated within the intervention arm, whereas resectability will be compared between the arms.

The anticipated prevalence of a pancreatic cancer diagnosis within 3-years of follow-up within this population is 1%³. Conservative estimates place the anticipated sensitivity of the Avantect test at 65% sensitivity and 95% specificity in the detection of PC. Under usual care in the UK, 10-20%^{13,14} of pancreatic cancer patients receive surgery with curative intent due to the majority (80%) presenting at Stage III or Stage IV¹⁵. Data from the CAPS cohort¹⁶ in the US has demonstrated that it is possible to reduce the proportion of patients presenting with late stage disease if surveillance testing is conducted on at-risk subgroups, thus improving the availability of curative resection as a treatment strategy. It is hoped that the Avantect test can improve the resectability of pancreatic cancers from a rate of 14% in usual care to 40% in the intervention arm (just over a 2.5-fold increase).

With three co-primary endpoints, each endpoint must be reached for an overall successful result. To achieve an overall power of 90%, the power for each endpoint should be $90\%^{(1/3)} = 96.5\%$. Following guidance from Korevaar and colleagues¹⁷, the analysis will consist of a one-sided test at an cumulative alpha of 0.05 at the final analysis. Because there is an interim analysis at stage 1 for efficacy and futility, the one-sided significance level changes at the interim and final analysis.

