An analysis for futility and efficacy will be conducted once 3,200 individuals randomised to the intervention arm have returned for the third blood-draw (T2) in order to obtain cancer outcome data from the cancer registry. This amounts to 43.8 % of the total information accrual in the intervention arm, accounting for 2.5% not qualifying for the Per Protocol population (see 9.4; $3,200/7,312$). All individuals with one or more Avantect “detected” test results will be included as positive predictions. Individuals whose Avantect test results are all “not detected” will be included as negative predictions. Based on a cumulative one-sided alpha of 0.05 and 96.5% power for the three co-primary outcomes, the futility and efficacy thresholds at stage 1 interim analysis are detailed in the table below. If all study endpoints are deemed futile, or in the scenario that all study endpoints are deemed efficacious the study will stop at this stage. If all of the study endpoints are deemed promising then the study will continue to stage 2. If there is a combination of results, the Trial Steering Committee (TSC) and IDMC will decide whether the study progresses to stage 2.

	Expected proportion	Futility threshold at stage 1	Promising result range at stage 1	Efficacy threshold at stage 1
Sensitivity	65%	<46.5%	46.5% to 63.1%	>63.1%
Specificity	95%	<92.0%	92.0% to 94.9%	>94.9%
Resectability	40%	<21.0%	21.0% to 38.1%	>38.1%

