9.3 STUDY TIMEPOINTS

There will be three timepoints for blood collection: at baseline (T0), 6 months +/- 2 weeks post-baseline (T1), and 12 months +/- 2 weeks from baseline (T2). For each study timepoint, the Avantect test will be conducted. For samples collected from participants assigned to the intervention arm, the Avantect test will be assessed as soon as possible within 14 business days of receipt of samples in the analysing laboratory at ClearNote Health. Those with positive test results (test result = Avantect “detected”) in the intervention arm will undergo diagnostic pancreas imaging. Samples collected from participants assigned to the Control arm will be stored for potential future Avantect testing or future research.

The study design comprises a pilot and two study stages:

- Stage 1 Analysis will be carried out 6 months after the T1 visit for 3,200 participants in the intervention arm. Only participants followed up for a minimum of 6 months after the T1 visit in the intervention arm will be included in this analysis.
- Stage 2 Analysis will be carried out after 3-year follow-up data has been collected for all 15,000 participants.

In addition, during the study annual readouts will be provided to the data monitoring committee to monitor study progress and inform on decisions to continue or stop the study.

The diagnostic performance of the Avantect test results will be summarised according to the pancreatic cancer diagnoses collected by the point of analysis. The stage shift, and resection rate of pancreatic cancer will be summarised by arm. For this purpose, a positive test at any timepoint will be considered a ‘positive prediction’ e.g., if a participant has a negative result at T0, but a positive result at T1, their overall prediction will be considered as at-risk of pancreatic cancer.

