9.4 STATISTICAL ANALYSIS PLAN (SAP)

This study will be analysed using the principles of the International Conference on Harmonisation E9 guidelines and reported according to the CONSORT guidelines. A full and detailed statistical analysis plan will be developed prior to the final analysis of the study. The main features of which are described here.

All analyses will be conducted on a Per Protocol population. All individuals in the control arm will qualify for the Per Protocol population. Individuals in the intervention arm will qualify for the Per Protocol population if they have at least one analysable Avantect test result (i.e. either “Detected” or “Not detected”). Per Protocol population will be analysed according to the original randomisation

group even when other aspects of the protocol are not followed e.g.unplanned cross-over, study withdrawal. It is expected that 98.8% of the randomised population will qualify for the Per Protocol population.

The co-primary outcomes are Avantect sensitivity and specificity in detecting PC, and resectability rate. Sensitivity is defined as the proportion of participants in the intervention arm with one (or more) Avantect “detected” test results who have pancreatic cancer diagnosed via imaging in relation to all individuals in the intervention arm who had pancreatic cancer diagnosed. Specificity is defined as the proportion of participants in the intervention arm with one or more Avantect “not detected” test results, and no Avantect “detected” results, who did not have a pancreatic cancer diagnosis in relation to all individuals in the intervention arm who did not have a pancreatic cancer diagnosis. Resectability is defined as the proportion of PCs deemed resectable by the study MDT divided by the number of PCs and will be compared between arms. For all co-primary endpoints, a logistic model will be used to estimate uncertainty. At the stage 1 interim analysis, due to alpha spending to reach a cumulative total alpha of 0.025 for each co-primary endpoint, a one-sided 98.6% confidence interval will be calculated to estimate the lower-bound of the observed proportion. At the stage 2 final analysis, a one-sided 98.5 % one-sided interval will be calculated instead. Co-primary endpoints will also be assessed for regular oversight meetings, where a one-sided 95% confidence interval will be used.

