At the stage 1 interim analysis, co-primaries will be considered ‘futile’, ‘promising’ or ‘efficacious’ according to the following table:

	Expected proportion	Futility threshold at stage 1	Promising result range at stage 1	Efficacy threshold at stage 1
Sensitivity	65%	<46.5%	46.5% to 63.1%	>63.1%
Specificity	95%	<92.0%	92.0% to 94.9%	>94.9%
Resectability	40%	<21.0%	21.0% to 38.1%	>38.1%

At the stage 2 final analysis, the sensitivity co-primary will be considered successful if a sensitivity of 49% can be ruled out with a one-sided p-value of 0.03 among participants in the intervention arm. Specificity will be considered successful if a specificity of 92% can be ruled out with a one-sided p-value of 0.03 among participants in the intervention arm. Resectability will be considered successful if the resectability rate in the intervention arm is higher than the rate in the control arm at a one-sided p-value of 0.03.

Secondary outcomes, in order of importance, are defined as follows, which all are calculated with a minimum of 90% power:

Stage shift - The analysis will be conducted by comparing the proportion of PC cases diagnosed at stage I/II vs III/IV between the intervention and control arms. A proportion of 60% (44/73 PCs) is expected in the intervention arm versus 35% (26/73 PCs) in the control arm, which provides 90% power at a one-sided alpha of 0.05. Stage shift will be considered successful if the proportion in the intervention arm is higher than the rate in the control arm at a one-sided p-value of 0.05.

PPV in detecting PC - The analysis will be conducted within the intervention arm. With a sample size of 7,500, PC prevalence of 1%, and 2.5% lost from the per protocol population, there will be an expected 410 individuals with an Avantect “detected - abnormal” result. 11.6% (48/410) are expected to have a PC. PPV will be considered successful if a null PPV of 5% can be ruled out at a one-sided p-value of 0.05.

NPV in ruling out PC - The analysis will be conducted within the intervention arm with a sample size of 7,500, PC prevalence of 1%, and 2.5% lost from the per protocol population, will be an expected 6,902 individuals without an Avantect “detected - abnormal” result. 99.6% (6,877/6,902) are expected to not have a diagnosis of PC. NPV will be considered successful if a null NPV of 99% can be ruled out at a one-sided p-value of 0.05.

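### Section 9.2 sets a cumulative one-sided alpha of 0.05 and section 9.4 sets 0.025; the intervals, the final p-value, the Stage 1 table and the stated power are drawn from a mixture of the two

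*Protocol*

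**What the plan says.** Section 9.2 (Sample size) states that "the analysis will consist of a one-sided test at an cumulative alpha of 0.05 at the final analysis". It introduces the Stage 1 threshold table with the same total: "Based on a cumulative one-sided alpha of 0.05 and 96.5% power for the three co-primary outcomes".

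Section 9.4 (Statistical Analysis Plan) gives another total for the same three endpoints: "due to alpha spending to reach a cumulative total alpha of 0.025 for each co-primary endpoint, a one-sided 98.6% confidence interval will be calculated". That interval is for Stage 1. For the final analysis, "a one-sided 98.5 % one-sided interval will be calculated instead".

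Later in section 9.4, each co-primary has a final success criterion at a one-sided p-value of 0.03. For resectability, the intervention rate must be "higher than the rate in the control arm at a one-sided p-value of 0.03". For sensitivity the null is 49%, and for specificity 92%.

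On other looks, section 9.3 says that "annual readouts will be provided to the data monitoring committee to monitor study progress and inform on decisions to continue or stop the study". Section 9.4 adds that the co-primaries will be assessed at regular oversight meetings with a one-sided 95% interval.

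**The concern.** A confirmatory design needs one type I error budget. Here the budget is stated twice with a factor of two between the figures, and each figure has its own consequences in the text. A final 98.5% one-sided interval corresponds to a test at 0.015, half the 0.03 written as the success level. A reader cannot tell which total governs, which interval belongs beside the declared result, or whether the stated power applies. Section 9.2 requires all three co-primaries to succeed, so doubt about one endpoint is doubt about the whole trial. If the choice is left until Stage 1 results exist, it will look driven by the data.

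**Working it through.** **Inputs.** Information fraction t = 3,200/7,312 = 0.438 (section 9.2). Resectability 14% v 40%, 73 cases per arm, power 96.5% (section 9.2). Interim and final interval levels 98.6% and 98.5%; final p 0.03; sensitivity null 49% (section 9.4). The protocol does not name a spending function. A Pocock-type function is assumed because it reproduces the printed levels.

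**1. The printed levels.** Interim spend = α·ln(1 + (e − 1)t), with ln(1 + 1.718 × 0.438) = 0.561. The final nominal level is solved from a bivariate normal with correlation √0.438.

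| Cumulative α | Interim level | Final level | As printed |
|---|---|---|---|
| 0.025 | 0.0140 | 0.0147 | 98.6% and 98.5% intervals |
| 0.05 | 0.0280 | 0.0311 | final p of 0.03 |

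Combining levels: 0.014 then 0.015 totals 0.025; 0.028 then 0.03 totals 0.049; the written mixture, 0.014 then 0.03, totals 0.038.

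**2. The 73 cases per arm.** Unpooled normal formula: n = (z₁₋α + z₀.₉₆₅)² × (0.14×0.86 + 0.40×0.60)/0.26².
- α = 0.03: (1.881 + 1.812)² × 0.3604/0.0676 = 72.7, so 73, as printed. Power at 73 is 96.6%.
- α = 0.015: (2.170 + 1.812)² × 0.3604/0.0676 = 84.5, so 85. Power at 73 is 93.7% (92.4% with pooled variance).

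The resectability sizing therefore belongs to the 0.05 scheme.

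**3. The Stage 1 table.** Take 32 cases (1% of 3,200) and Wald lower limits of the expected proportions.
- At 0.014 (z = 2.197): 0.65 − 2.197√(0.65×0.35/32) = 46.5%, and 0.40 − 2.197√(0.40×0.60/32) = 21.0%. These are the printed futility limits.
- At 0.028 (z = 1.911): about 48.9% and 23.4%.

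So section 9.2 attributes to alpha 0.05 two limits that come from the 0.025 scheme.

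The specificity efficacy bound follows from neither level. With 3,168 non-cases (99% of 3,200) and a 92% null, 0.92 + z√(0.92×0.08/3,168) is 93.1% at 0.014 and 92.9% at 0.028. The printed bound is 94.9%.

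**4. Can the reported interval contradict the verdict?**
- Sensitivity 45/73 = 61.6% against 49%. Score z = (0.6164 − 0.49)/√(0.49×0.51/73) = 2.16, p = 0.015; exact p = 0.020. Both pass 0.03. On the logit scale, ln(45/28) = 0.474 with standard error √(1/45 + 1/28) = 0.241. The 98.5% lower bound is 0.474 − 2.170×0.241 = −0.048, which is 48.8% and does not exclude 49%. This is not caused by mixing methods: the logit-scale test itself gives p = 0.016.
- Resectability 20/73 v 10/73. Pooled z = 0.137/0.0669 = 2.05, p = 0.020. This passes 0.03 and fails 0.015.

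**5. The sensitivity null.** Section 9.2 states power against 42%; section 9.4 tests 49%. With 73 cases and true sensitivity 65% (normal approximation), power against 49% is about 81% at 0.03 and 72% at 0.015. Choosing an alpha does not by itself settle sensitivity.

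**The case against.** The best reply is that the protocol has only one final success rule. Section 9.4 words p=0.03 as the criterion for all three endpoints, and the intervals are there to express uncertainty. That is correct. A reader might infer that the protocol contains two competing pass/fail rules, but no sentence makes the 98.5% limit a criterion. What remains is that the interval is presented as the product of alpha spending to a stated total, and that total conflicts with section 9.2 and with the 0.03.

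A reader might also infer that the Stage 1 bounds fit neither scheme. That is not so: two futility limits match the 0.014 level exactly. The resectability efficacy bound of 38.1% also equals a pooled two-arm bound against 14% with 32 cases per arm at 0.014. That match may be coincidence, because section 9.2 places the Stage 1 assessment within the intervention arm. The strict specificity bound makes early stopping harder and does not raise type I error.

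Finally, a reader might infer that the annual readouts inflate the error rate. The documents do not support a figure. Section 9.3 does not say that a readout can stop the trial for efficacy, and stopping for futility or safety would not inflate type I error. The 95% intervals are tied to oversight meetings that the protocol does not equate with the readouts. Section 7.6.4 schedules only three registry downloads, and the data monitoring committee's charter is not shown. What stands is that the role of these looks is not stated.

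**Conclusion.** The protocol is wrong as written: two cumulative alphas are given for the same endpoints, and the dependent figures are split between them. The 98.6% and 98.5% intervals and the 46.5% and 21.0% futility limits belong to 0.025. The final p of 0.03 and the 73 cases per arm belong to 0.05. Taken literally, interim 0.014 with final 0.03 spends about 0.038 per endpoint.

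If 0.025 governs, resectability power at 73 cases is about 93.7% (unpooled), not 96.5%. If 0.05 governs, the power stands, but the intervals and those futility limits do not.

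The spending levels rest on an assumed Pocock-type function, the power figures on normal approximations, and the Stage 1 limits on 32 interim cases. The conflict between 0.05 and 0.025, and between 98.5% and 0.03, needs no assumption. No inflation from the annual readouts is claimed.

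**What to change.** Choose one cumulative one-sided alpha and use it throughout sections 9.2 and 9.4, before any Stage 1 outcome data are seen.

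- **If 0.05:** delete 0.025 from section 9.4, change the one-sided intervals to about 97.2% (Stage 1) and 97% (final), keep p=0.03, and recompute the Stage 1 table. The 73 cases per arm stand.
- **If 0.025:** change the final p-value to about 0.015, correct both statements of 0.05 in section 9.2, and restate resectability power at 73 cases as about 93–94%. Keeping 96.5% would need 85 cases per arm, or 88 after the 2.5% loss (85/0.975 = 87.2, rounded up). At 1% prevalence that is about 8,800 per arm, 17,600 in total against 15,000.

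Under either choice, name the spending function, state how each Stage 1 bound is derived (including 94.9% for specificity), and restate sensitivity power against a single null, 42% or 49%. Also state that the annual readouts and the 95% intervals at oversight meetings are not used to stop for efficacy.

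The cost is protocol wording and one recalculated table. There is no recruitment cost unless 0.025 is chosen and the original power is kept; otherwise 0.025 costs about three percentage points of resectability power.

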7. STUDY PROCEDURES

7.1 SCHEDULE OF OBSERVATIONS AND PROCEDURES

Visit:	Baseline (T0)	T1	T2	T3
Time:	Within 6 months from Diabetes mellitus (DM) diagnosis*	6 months after T0	12 months after T0	Three occasions over the study duration from consent (T0)
Eligibility evaluation	X			

Informed consent	X			
Patient Data Collection Interview ^a	X			
STAI questionnaire ^b	X	X	X	
Blood sample collection ^c	X	X	X	
Body measurements ^d	X	X	X	
Electronic Health Record Review ^e	X	X	X	
Cancer and mortality registry review				X

NB: The participant/legal representative is free to withdraw consent at any time without providing a reason. When withdrawn, the participant will continue to receive standard clinical care. Follow up data will continue to be collected (unless the participant/legal representative has specifically stated that they do not want this to happen).

*In the SAFE-D study “date of DM diagnosis” refers to the elevated HbA1c date

a: sex, ethnicity, selected pre-existing conditions of interest, family history of cancer, smoking, vaping, alcohol use

b: 6-item STAI

c: 2x10 mL Streck® tubes, 1x6 mL lithium heparin tube

d: height, weight, waist circumference

e: review of selected pre-existing conditions of interest from EHR summaries when available or participant self-reported.

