7.6.4 Timepoint T3 (2 years after T2)

T3 refers to the three years of follow-up (following recruitment at T0) which will be collected via linkage with the cancer and mortality registry. At the time of writing the cancer registry is managed by the National Cancer Registration and Analysis Service which sits within NHS England, and the mortality register is managed by the Office for National Statistics but can be accessed through NHS England. Cancer and mortality registry data will still be required and sought even if the owner of the dataset changes in the future. A cancer and mortality registry download will be obtained on three

occasions: once 6,400 participants have been recruited, once 15,000 participants have been recruited, and at 3 years post last participant recruited.

Data Collection from Cancer Registry:

- Any cancer diagnosis (ICD10 C00-D48)
- Date of cancer diagnosis
- Site of cancer diagnosis
- Stage of cancer at diagnosis
- Histology of cancer
- Survival status
- Cancer treatments

Data Collection from Mortality Registry:

[figure not shown]
- Date of death
- Causes of death

The local site study team will collect and keep NHS number, address and contact details (including 1 or 2 phone numbers and an email address) from all participants. NHS numbers and dates of birth for all participants will be shared securely by site to the SCTU. SCTU will then pass on the NHS numbers and dates of birth to the administrators at the registries to allow them to perform registry searches on three occasions during the study. The local site team will also share with the SCTU study team, via secure email, the contact details (name, postal and email address) for a select number of participants (numbers to be defined) who have consented to optional further research questionnaire.

Addresses will be used by sites to contact participants with any Avantect “Detected” results by post. Phone numbers will be used by sites to contact participants if required throughout the study, including contacting participants to inform them of a “Detected” Avantect test if deemed more appropriate than by post alone (at the discretion of the clinical team).

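### Oversight readouts of sensitivity are biased upward, and control-arm counts absent or out of date, because test-missed and control-arm cancers have no designed source except three registry downloads

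*Protocol*

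**What the plan says.** **Readouts.** Protocol 9.4, after setting the interval levels for the stage 1 and stage 2 analyses, adds: "Co-primary endpoints will also be assessed for regular oversight meetings, where a one-sided 95% confidence interval will be used". Section 9.3 says that "annual readouts will be provided to the data monitoring committee to monitor study progress and inform on decisions to continue or stop the study". It continues: "The diagnostic performance of the Avantect test results will be summarised according to the pancreatic cancer diagnoses collected by the point of analysis".

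**How cancers become known.** Participants with a positive test "in the intervention arm will undergo diagnostic pancreas imaging" (9.3). Sections 7.8.1 and 7.9.2 describe the urgent referral and the collection of imaging and pathology reports. A participant whose result is not detected simply carries on with study visits (7.8.2). For everyone else, cancer diagnoses come from registry downloads on three occasions: "once 6,400 participants have been recruited, once 15,000 participants have been recruited, and at 3 years post last participant recruited" (7.6.4).

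**Other contacts.** The record check at T0, T1 and T2 is a "review of selected pre-existing conditions of interest from EHR summaries when available or participant self-reported" (7.1). Adverse event reporting runs to 7 days after each study procedure (8.5.1.4). Neither is built to find a new pancreatic cancer.

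**Endpoints.** The sensitivity denominator is "all individuals in the intervention arm who had pancreatic cancer diagnosed" (9.4), so it includes the cancers the test missed. Resectability for the study endpoint rests on study-team review of MRI and CT scans (7.9.4).

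**The concern.** Sensitivity is detected cancers divided by detected plus missed cancers. At an oversight readout the detected cancers are nearly up to date, while the missed ones are only as recent as the last registry download. Before the first download the denominator contains almost nothing but detected cancers, so the ratio tends to 100% however poor the test is. Between later downloads the ratio stays too high, and control-arm cancers are counted only to the last download.

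The protocol recognises the asymmetry elsewhere. Section 9.2 confines the stage 1 interim to the intervention arm because more is known about that arm's diagnostic status, and ties its timing to obtaining registry outcomes. The oversight readouts carry neither safeguard. A committee could receive a sensitivity that flatters the test, with an interval that reflects only the number of known cancers, while deciding whether to continue.

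**Working it through.** **1. The plan's own figures (9.2).** 75 cancers per arm less 2.5% gives 73. At 65% sensitivity, 0.65 × 73 = 47.5, shown as 48 detected and 25 missed; 48/73 = 65.8%.

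**2. Calendar.** The pilot enrols 800 in 6 months. The other 14,200 enrol over 30 months, or 473.3 a month. The 6,400th participant enters at 6 + 5,600/473.3 = 17.8 months. The downloads in 7.6.4 therefore fall at about months 17.8, 36 and 36 + 36 = 72. Section 9.2 links registry outcomes to 3,200 intervention participants returning for T2, about 17.8 + 12 = 29.8 months.

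**3. Assumptions not in the documents.** Clinical diagnosis is uniform over 36 months from entry, or over 18 months (section 4 says most cancers appear within 12-18 months of diabetes diagnosis). Detected cancers are spread equally over T0, T1 and T2 and known 1.5 months after the test. In the base case there is no registry delay and no site capture of missed or control-arm cancers.

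**4. Formulas.** With D(t) the detected cancers known at month t, M(t) the missed cancers diagnosed by t, and L the latest download up to t:

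- readout = D(t) / [D(t) + M(L)]
- with complete linkage = D(t) / [D(t) + M(t)]

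**5. Expected counts, 7.6.4 timing, design sensitivity (48 detected, 25 missed).**

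| Month | Detected known | Missed known / diagnosed | Readout | If complete | Control known / diagnosed |
|---|---|---|---|---|---|
| 12 | about 3.8 | 0 / 0.7-1.4 | 100% | 72-84% | 0 / 2-4 |
| 24 | about 18.5 | 2.1-4.1 / 4.3-8.4 | 82-90% | 69-81% | 6-12 / 13-25 |
| 36, after download | about 36.7 | 11.1-17.9 / same | 67-77% | 67-77% | 32-52 / same |
| 60 | 48 | 11.1-17.9 / 23.4-25.0 | 73-81% | 66-67% | 32-52 / 68-73 |
| 72 | 48 | 25 / 25 | 65.8% | 65.8% | 73 / 73 |

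Month 24 in full. Early diagnosis: 18.5/(18.5 + 4.1) = 82%, against 18.5/(18.5 + 8.4) = 69%. Uniform diagnosis: 6.1 control cancers are known, so missed cancers known are 6.1 × 25/73 = 2.1 and the readout is 18.5/(18.5 + 2.1) = 90%, against 18.5/(18.5 + 4.3) = 81%. Month 72 returns the plan's 65.8%.

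**6. Splitting the month-24 excess.** The download schedule contributes 81.7 − 68.7 = 13.0 points (early) or 89.9 − 81.1 = 8.8 points (uniform). The rest, 68.7 − 65.8 = 2.9 or 81.1 − 65.8 = 15.3 points, is lead time: detected cancers surface before missed ones even when linkage is complete.

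**7. Varying the assumptions.** A 6-month registry delay raises month 24 to 93-96% and months 48-60 to 78-87%. If sites learn of half the early missed cancers at T1 or T2, month 12 reads 94-97%, and month 24 reads 79-91% across both delay settings.

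**8. Other true values.** A simulation used Poisson counts, diagnosis uniform over 36 months or 80% within 15 months, detected cancers known 2 months after the test, and no registry delay or site capture. The value 42% is the one 9.2 sets out to rule out (9.4 gives 49%).

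- Month 12: 100% whatever the true value. With half the early missed cancers captured by sites, a true 42% reads 90-93%.
- Month 24, true 65%: about 84-91%. The expected counts above put the low end at 82%; with complete linkage the two models together give about 69-82%.
- Month 24, true 42%: about 67-79%, against 51-63% if complete.
- Month 60, true 42%: about 52-62%, against 42-44% if complete.
- First download at month 29.8 instead: month 24 reads 100%.

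**9. The interval.** With 4 of 4 cancers detected at month 12, the exact one-sided 95% lower bound is 0.05^(1/4) = 47%. It reflects the small count, not the missing cancers. The logistic model named in 9.4 has no finite estimate there.

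**10. Resectability.** It needs study-team scan review (7.9.4). The registry items in 7.6.4 include stage and treatments, but neither scans nor resectability status, and no explicit route collects control-arm scans.

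**The case against.** - **The link is inferred.** Section 9.3 does not list what the annual readouts contain, and 9.4 does not call the oversight meetings annual or decision-making. The sentence on diagnoses collected so far may describe only the stage 1 and 2 analyses. Numerical thresholds exist only at stage 1, and 13.3 leaves statistical issues to the IDMC charter, which is not shown. This stands: reading 9.3 with 9.4 is natural, but it is not an explicit statement.
- **Near-100% at every readout.** A reader might infer this. It holds only before the first download; later figures are lower, as the table shows.
- **A failing test would almost surely look successful.** Just before a month-36 download, the simulation has a true 42% reading 79-88%, with the lower bound above 49% in 95-100% of runs. That needs the 7.6.4 timing and a readout on the eve of the download. With a first download at month 29.8 the figure falls to 53-65%, and straight after the month-36 download it equals complete ascertainment. The documents do not place a readout on either side, so this result is not relied on.
- **No control comparison at all.** This is true before the first download if sites report nothing. Afterwards counts exist but are out of date.
- **Sites may hear of missed cancers.** They may, and this shrinks the bias without removing it.
- **Late readouts have little left to stop.** Recruitment ends at month 36 and the last T2 visit is near month 48. This stands, and it puts the practical weight on the earlier readouts.

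**Conclusion.** The point holds. If sections 9.3 and 9.4 are followed together, sensitivity at oversight readouts is biased upward and control-arm counts are absent or out of date. The direction follows from the data routes; the size rests on the assumed diagnosis times, registry delay and site capture, none of which the documents give.

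The bias is greatest before the first download. At month 24 under the 7.6.4 timing, the part due to the download schedule is about 9-13 points at the design sensitivity; lead time adds to it and would remain with complete linkage. If the first download follows the 9.2 trigger instead, the uninformative period extends to about month 30. Specificity and PPV are barely affected. No numerical stopping boundary is attached to these readouts, so this is a correction that should be made rather than a flaw in the planned stage 1 or stage 2 tests. It is separate from any question of alpha spent at these looks.

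**What to change.** In 9.3 and 9.4, and in the IDMC charter:

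- For oversight readouts of sensitivity, NPV, stage shift and resection, apply one cut-off to every cancer in both arms. Count only cancers diagnosed up to the latest registry download, in participants with the required follow-up at that date.
- Show none of these before the first download.
- Do not show between-arm resectability until control-arm scans have been obtained and reviewed by the study team. The common cut-off alone does not supply them.
- State that sensitivity and between-arm resectability at these readouts do not inform stopping.
- Keep specificity, PPV, imaging outcomes and safety at every readout. With the cut-off figures, this still lets the committee monitor main outcomes as 13.3 requires.
- Reconcile the first download in 7.6.4 with the stage 1 trigger in 9.2.

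The cost is a few sentences and a charter entry. The committee sees sensitivity and between-arm figures less often. No participants are added, and the tests planned for stages 1 and 2 do not change.
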